11.3 Time-to-event definition

- Progression-Free Survival (PFS) is defined as the duration of time from start of treatment to time of objective disease progression (including initiation of new therapy or death).

11.4 Relapsed/Refractory definitions

Refractory disease: Disease that is non-responsive (failure to achieve minimal response or development of progressive disease (According to the Sixth International Workshop on WM) while on therapy), or progresses within 60 days of last therapy.

Relapsed disease: Previously treated disease that progresses (According to the Sixth International Workshop on WM) while on therapy) and requires initiation of new therapy that does not meet criteria for refractory.

12. DATA REPORTING / REGULATORY REQUIREMENTS

Adverse event lists, guidelines, and instructions for AE reporting can be found in Section 7.0 (Adverse Events: List and Reporting Requirements).

12.1 Data Reporting

12.1.1 Method

The Office of Data Quality (ODQ) will collect, manage, and perform quality checks on the data for this study.

12.1.2 Responsibility for Data Submission

Investigative sites within DF/HCC or DF/PCC are responsible for submitting data and/or data forms to the Office of Data Quality in accordance with DF/HCC SOPs.

12.2 Data Safety Monitoring

The DF/HCC Data and Safety Monitoring Committee (DSMC) will review and monitor toxicity and accrual data from this study. The committee is composed of clinical specialists with experience in oncology and who have no direct relationship with the study. Information that raises any questions about participant safety will be addressed with the Overall PI and study team.

The DSMC will review each protocol up to four times a year or more often if required to review

toxicity and accrual data. Information to be provided to the committee may include: up-to-date participant accrual; current dose level information; DLT information; all grade 2 or higher unexpected adverse events that have been reported; summary of all deaths occurring within 30 days of intervention for Phase I or II protocols; for gene therapy protocols, summary of all deaths while being treated and during active follow-up; any response information; audit results, and a summary provided by the study team. Other information (e.g. scans, laboratory values) will be provided upon request.

12.3 Multicenter Guidelines

This protocol will adhere to the policies and requirements of the DF/HCC Multi-Center Data and Safety Monitoring Plan.

- The Overall PI/Coordinating Center is responsible for distributing all IND Action Letters or Safety Reports to all participating institutions for submission to their individual IRBs for action as required.
- Mechanisms will be in place to ensure quality assurance, protocol compliance, and adverse event reporting at each site.
- Except in very unusual circumstances, each participating institution will order the study agent(s) directly from supplier. A participating site may order the agent(s) only after the initial IRB approval for the site has been forwarded to the Coordinating Center.

12.4 Collaborative Agreements Language

Not applicable

13. STATISTICAL CONSIDERATIONS

This is a phase II single-arm, open-label prospective study aimed at evaluating the efficacy of daratumumab, an anti-CD38 monoclonal antibody, in patients with relapsed and/or refractory WM. With a double-sided alpha of 0.04 and power of 0.92, a sample size of 30 patients would suffice to show a statistical difference between the alternative hypothesis of obtaining an ORR of 70% versus the null hypothesis of obtaining an ORR of 40%. If 18 patients or more obtain a response, then daratumumab will continue further evaluation. If 17 patients or less obtain a response, then daratumumab should not continue further evaluation. The critical value of 18 means to include 70% as the upper level of the 95% CI, while the critical value of 6 patients means to exclude 40% as the upper level of 95% CI based on an exact binomial estimate (STATA SE 13.1). In addition, assuming that an adverse event associated with study drug has a true incidence of 10%, with an estimated sample size of 30 patients, the likelihood of observing at least 1 adverse event would be at least 95%

13.1 Study Design/Endpoints

This is a phase II single-arm, open-label prospective study aimed at evaluating the efficacy and

safety of daratumumab in patients with relapsed and/or refractory WM. With a double-sided type I error of 4% and power of 92%, a sample size of 30 patients would suffice to show a statistical difference between the alternative hypothesis of obtaining an ORR (see section 1.2) of 70% versus the null hypothesis of obtaining an ORR of 40%. If 18 patients or more obtain a response, then daratumumab will continue further evaluation. If 17 patients or less obtain a response, then daratumumab should not continue further evaluation. The primary endpoint is ORR. Secondary endpoints include MR, PR, VGPR, CR and PFS.

13.2 Sample Size, Accrual Rate and Study Duration

A total of 30 patients will be accrued. Accrual time will be approximately 1 year, at a rate of 2-3 patients per month. The individual study duration will be approximately 1.5 years. Patients will then be followed up for 2 years after completion or discontinuation of therapy or until death, whichever occurs first. The total study duration will be approximately 4.5 years (1 year of accrual, 1.5 years of therapy and 2 years of follow-up). The individual study duration will be approximately 3.5 years (1.5 years of therapy and 2 years of follow-up).

Accrual Targets				
Ethnic Category	Sex/Gender			
	Females		Males	Total
Hispanic or Latino	1	+	4	= 5
Not Hispanic or Latino	5	+	20	= 25
Ethnic Category: Total of all subjects	6 (A1)	+	24 (B1)	= 30 (C1)
Racial Category				
American Indian or Alaskan Native		+		=
Asian		+	1	= 1
Black or African American	1	+	1	= 2
Native Hawaiian or other Pacific Islander		+		=
White	5	+	22	= 27
Racial Category: Total of all subjects	6 (A2)	+	24 (B2)	= 30 (C2)

(A1 = A2)

(B1 = B2)

(C1 = C2)

13.3 Stratification Factors

No stratification factors will be applied to any analysis.

13.4 Interim Monitoring Plan

Please refer to section 13.1 and 13.2.

13.5 Analysis of Primary Endpoints

Primary analysis will be performed in the Full Analysis Set (FAS) for the primary assessment of efficacy. The FAS will include those participants who have received at least one dose of therapy. The primary analysis will include calculating the proportion of patients having at least a 25% reduction in serum IgM (minor response or better) at any point on therapy. Confidence intervals (95%) around these point estimates will be presented.

13.6 Analysis of Secondary Endpoints

Secondary analyses will be performed in the FAS. Time to progression (TTP) will be estimated using Kaplan Meier methodology with median time plus 25th and 75th percentile along with 95% confidence intervals, as appropriate.

Minor, partial, very good partial, and complete response rates will be estimated in the FAS population by calculating the proportion of patients having those responses and calculating the 95% confidence intervals around these point estimates.

All participants who receive at least one dose of daratumumab during the study will be included in the safety analysis.

13.7 Reporting and Exclusions

13.7.1 Evaluation of Toxicity

All participants who receive at least one dose of any test material during the study will be included in the safety analysis.

13.7.2 Evaluation of the Primary Efficacy Endpoint

All participants included in the study must be assessed for response to treatment, even if there are major protocol treatment deviations or if they are ineligible. Each participant should be assigned a response category based on the response criteria in Section 9.1.2. According to section 11.1.2, patients who underwent plasmapheresis less than 4 weeks prior to response assessment will be deemed non-evaluable, according to Section 11.1.2.

All participants who met the eligibility criteria and were enrolled in the trial will be included in the main analysis of the response rate. All conclusions will be based on all eligible participants.

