4. REGISTRATION PROCEDURES

4.1 General Guidelines for DF/HCC Institutions

Institutions will register eligible participants in the Clinical Trials Management System (CTMS) OnCore. Registrations must occur prior to the initiation of protocol therapy. Any participant not registered to the protocol before protocol therapy begins will be considered ineligible and registration will be denied.

An investigator will confirm eligibility criteria and a member of the study team will complete the protocol-specific eligibility checklist.

Following registration, participants may begin protocol therapy. Issues that would cause treatment delays should be discussed with the Overall Principal Investigator (PI). If a participant does not receive protocol therapy following registration, the participant's registration on the study must be canceled. Registration cancellations must be made in OnCore as soon as possible.

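### Sections 13.5 and 13.7.2 name different primary sets for the response rate, and the 18-responder rule is tied to neither

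*Combined protocol and SAP*

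**What the plan says.** Section 13.5 states "Primary analysis will be performed in the Full Analysis Set (FAS) for the primary assessment of efficacy" and defines the set by dosing alone: "The FAS will include those participants who have received at least one dose of therapy". Section 13.6 uses the same set for the other response rates and for time to progression: "Secondary analyses will be performed in the FAS".

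Section 13.7.2, headed as the evaluation of the primary efficacy endpoint, uses a different criterion: "All participants who met the eligibility criteria and were enrolled in the trial will be included in the main analysis of the response rate". It follows this with "All conclusions will be based on all eligible participants". Earlier in the same section, response must be assessed in all participants, "even if there are major protocol treatment deviations or if they are ineligible", so an ineligible patient who was treated will have a recorded response.

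The decision rule in Section 13.1, repeated in the opening of Section 13, is a bare count: "If 18 patients or more obtain a response, then daratumumab will continue further evaluation", and 17 or fewer means that evaluation stops. It speaks of patients, follows a sample size of 30, and names no analysis set.

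**The concern.** Two sections give different answers on who is in the primary response analysis, and both claim authority over the result: one through the primary assessment of efficacy, the other through all conclusions. The trial is single-arm and open-label with a fixed cut. If the sets differ, someone would have to choose between them after the responses are known, and the choice could decide whether the drug goes forward.

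The documents foresee such a difference. Section 13.7.2 itself mentions ineligible participants. In the multi-center plan, Section 17.7.3 allows eligibility exceptions with IRB approval, and Section 17.8.2 defines an exception as enrolling someone who does not meet all the criteria. A patient enrolled that way is in the FAS from the first dose and outside the eligible set, without any late discovery.

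**Working it through.** **Inputs.** N = 30, cut at 18 responders, null 40%, alternative 70%, two-sided type I error 4%, power 92% (Section 13.1); accrual of 30 with no allowance for ineligible patients (Section 13.2). The number m of ineligible patients among the 30 treated is not in the documents. I take m = 1 and m = 2 as assumptions, with ineligibility independent of response.

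**Reproducing the plan's figures.** With X ~ Binomial(30, p):

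- Power: P(X ≥ 18 | p = 0.70) = 0.9155, against the stated 92%.
- Upper-tail error: P(X ≥ 18 | p = 0.40) = 0.0212. Adding the lower tail at the plan's other critical value, P(X ≤ 6 | p = 0.40) = 0.0172, gives 0.0384. Doubling the upper tail gives 0.0425. Both round to the stated 4%.

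The design figures are therefore sound for a denominator of 30.

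**Direction of the effect.** Registration of an untreated participant is cancelled: "If a participant does not receive protocol therapy following registration, the participant's registration on the study must be canceled" (Section 4.1, and likewise Section 4.3). The eligible set is thus in effect a subset of the FAS. Dropping patients can only lower the responder count. Moving from the FAS to the eligible set can turn go into no-go, never the reverse.

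**A single case.** One ineligible responder, with exact (Clopper-Pearson) 95% intervals:

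- FAS: 18/30 = 60.0%, interval 40.6% to 77.3%, go.
- Eligible set: 17/29 = 58.6%, interval 38.9% to 76.5%, no-go. The lower limit also falls below the 40% null.

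**Probability of conflicting verdicts.** A go on the eligible set implies a go on the FAS, so

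P(conflict) = P(X₃₀ ≥ 18) − P(X₃₀₋ₘ ≥ 18).

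- m = 1, p = 0.70: 0.9155 − 0.8706 = 0.0449.
- m = 2, p = 0.70: 0.9155 − 0.8087 = 0.1069 (difference taken before rounding).
- m = 1, p = 0.40: 0.0212 − 0.0135 = 0.0078 (before rounding).
- m = 2, p = 0.40: 0.0212 − 0.0081 = 0.0131.
- At p = 0.60, an intermediate value and not a plan hypothesis: 0.0884 for m = 1 and 0.1799 for m = 2.
- With m = 0 the verdicts always agree.

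**Operating characteristics with the cut kept at 18:**

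| Patients in the set | False-go rate at 40% | Power at 70% |
|---|---|---|
| 30 | 2.1% | 91.6% |
| 29 | 1.3% | 87.1% |
| 28 | 0.8% | 80.9% |

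**The case against.** The strongest reply is that the two sets are meant to be the same people. Section 1.1 enrolls and treats those who meet the criteria, Section 4 registers only eligible participants and cancels untreated registrations, and exceptions need prior IRB approval. For outside sites the coordinating center checks eligibility before registration, and Section 19.1 adds a review within 30 days of enrollment. Ineligible treated patients should be uncommon. That stands, and it means the probabilities above are conditional on at least one such patient. If each treated patient instead had an assumed independent 0.5% to 2% chance of being ineligible, the overall probability of conflicting verdicts would be 0.7% to 3.0% at 70%, 1.3% to 5.3% at 60% and 0.1% to 0.4% at 40%.

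It can also be said that the sentence on the main analysis only lists who is included and does not exclude anyone. Taken alone, that is fair, but the next sentence bases all conclusions on eligible participants and cannot be squared with Section 13.5.

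Lastly, the rule follows directly on a sample size of 30, so the natural reading is 18 of the 30 treated. I agree that this is the likely intent, but no text says so, and the sentence on conclusions points the other way.

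How patients who cannot be evaluated for response enter the denominator, and what the cut becomes if the set is not exactly 30, are separate gaps that do not affect this point.

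**Conclusion.** The concern holds. This is a conflict between two stated rules for the same endpoint, not an omitted detail, and nothing in the plan resolves it. It has no effect if every treated patient is eligible. With one or two ineligible patients, assumed unrelated to response, the verdicts conflict with probability 4.5% or 10.7% at the alternative and 0.8% or 1.3% at the null. The harm runs one way: applying the rule to the eligible set costs about 4 or 11 points of power (91.6% to 87.1% or 80.9%) and does not inflate the false-go rate. It should be fixed because the consequence is an undecidable go/no-go in a close case, even though the event should be rare.

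**What to change.** In Sections 13.5 and 13.7.2, name the FAS (at least one dose) as the single primary set, and state that both the response rate and the 18-responder rule are read on it. This fits the calculation on 30 patients and the set already used in Section 13.6. Delete the sentence in 13.7.2 that bases all conclusions on eligible participants, and report the eligible set as a sensitivity analysis.

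In the same edit, correct two references in 13.7.2 to sections that do not exist: 9.1.2 should point to Section 11.2 (response criteria) and 11.1.2 to Section 11.1 (evaluability after plasmapheresis).

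The cost is a wording amendment to Section 13 with IRB approval. It needs no new data, visits or patients.

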APPENDIX A PERFORMANCE STATUS CRITERIA

ECOG Performance Status Scale		Karnofsky Performance Scale	
Grade	Descriptions	Percent	Description
0	Normal activity. Fully active, able to carry on all pre-disease performance without restriction.	100	Normal, no complaints, no evidence of disease.
		90	Able to carry on normal activity; minor signs or symptoms of disease.
1	Symptoms, but ambulatory. Restricted in physically strenuous activity, but ambulatory and able to carry out work of a light or sedentary nature (e.g. , light housework, office work).	80	Normal activity with effort; some signs or symptoms of disease.
		70	Cares for self, unable to carry on normal activity or to do active work.
2	In bed <50% of the time. Ambulatory and capable of all self-care, but unable to carry out any work activities. Up and about more than 50% of waking hours.	60	Requires occasional assistance, but is able to care for most of his/her needs.
		50	Requires considerable assistance and frequent medical care.
3	In bed >50% of the time. Capable of only limited self-care, confined to bed or chair more than 50% of waking hours.	40	Disabled, requires special care and assistance.
		30	Severely disabled, hospitalization indicated. Death not imminent.
4	100% bedridden. Completely disabled. Cannot carry on any self-care. Totally confined to bed or chair.	20	Very sick, hospitalization indicated. Death not imminent.
		10	Moribund, fatal processes progressing rapidly.
5	Dead.	0	Dead.

NCI Protocol #:N/A
DF/HCC Protocol #: 17-164
Protocol Version Date: 2.1.19

**APPENDIX B DANA-FARBER/HARVARD CANCER CENTER MULTI-CENTER OVERSIGHT PLAN
AND DATA AND SAFETY MONITORING PLAN VERSION 2 8.2.2017**

DFCI IRB Protocol #:17-164

TABLE OF CONTENTS

15.	INTRODUCTION.....	39
15.1	Purpose.....	39
15.2	Multi-Center Data and Safety Monitoring Plan Definitions.....	39
16.	GENERAL ROLES AND RESPONSIBILITIES	40
16.1	DF/HCC Sponsor.....	40
16.2	Coordinating Center.....	41
16.3	Participating Institution.....	41
17.	DF/HCC REQUIREMENTS FOR MULTI-CENTER PROTOCOLS	42
17.1	Protocol Distribution.....	42
17.2	Protocol Revisions and Closures.....	42
17.3	Informed Consent Requirements.....	43
17.4	IRB Documentation.....	43
17.5	IRB Re-Approval.....	44
17.6	Participant Confidentiality and Authorization Statement.....	44
17.7	DF/HCC Multi-Center Protocol Registration Policy.....	44
17.8	DF/HCC Protocol Case Number.....	45

15. INTRODUCTION

The Dana-Farber/Harvard Cancer Center Multi-Center Data and Safety Monitoring Plan (DF/HCC DSMP) outlines the procedures for conducting a DF/HCC Multi-Center research protocol. The DF/HCC DSMP serves as a reference for any sites external to DF/HCC that are participating in a DF/HCC clinical trial.

15.1 Purpose

To establish standards that will ensure that a Dana-Farber/Harvard Cancer Center Multi-Center protocol will comply with Federal Regulations, Health Insurance Portability and Accountability Act (HIPAA) requirements and applicable DF/HCC Standard Operating Procedures.

15.2 Multi-Center Data and Safety Monitoring Plan Definitions

DF/HCC Multi-Center Protocol: A research protocol in which one or more outside institutions are collaborating with Dana-Farber/Harvard Cancer Center where a DF/HCC investigator is the sponsor. DF/HCC includes Dana-Farber/Partners Cancer Care (DF/PCC) Network Clinical Trial Affiliates.

Lead Institution: One of the Dana-Farber/Harvard Cancer Center consortium members (Dana-Farber Cancer Institute (DFCI), Massachusetts General Hospital (MGH), Beth Israel Deaconess Medical Center (BIDMC), Boston Children's Hospital (BCH), Brigham and Women's Hospital (BWH) responsible for the coordination, development, submission, and approval of a protocol as well as its subsequent amendments per the DFCI IRB and applicable regulatory guidelines (CTEP, Food and Drug Administration (FDA), Office of Biotechnology Activities (OBA) etc.). The Lead Institution is typically the home of the DF/HCC Sponsor. The Lead Institution also typically serves as the Coordinating Center for the DF/HCC Multi-Center Protocol.

DF/HCC Sponsor: The person sponsoring the submitted Multi-Center protocol who takes responsibility for initiation, management and conduct of the protocol at all research locations. In applicable protocols, the DF/HCC Sponsor will serve as the single liaison with any regulatory agencies (i.e. FDA). The DF/HCC Sponsor has ultimate authority over the protocol and is responsible for the conduct of the study at DF/HCC and all Participating Institutions. In most cases the DF/HCC Sponsor is the same person as the DF/HCC Overall Principal Investigator; however, both roles can be filled by two different people.

Participating Institution: An institution that is outside the DF/HCC and DF/PCC consortium that is collaborating with DF/HCC on a protocol where the sponsor is a DF/HCC Investigator. The Participating Institution acknowledges the DF/HCC Sponsor as having the ultimate authority and responsibility for the overall conduct of the study.

Coordinating Center: The entity (i.e. Lead Institution, Medical Monitor, Contract Research Organization (CRO), etc) that provides administrative support to the DF/HCC Sponsor in order that he/she may fulfill the responsibilities outlined in the protocol

document and DSMP, and as specified in applicable regulatory guidelines (i.e. CTEP Multi-Center Guidelines). In general, the Lead Institution is the Coordinating Center for the DF/HCC Multi-Center Protocol.

DF/HCC Office of Data Quality (ODQ): A group within DF/HCC responsible ensuring high-quality standards are used for data collection and the ongoing management of clinical trials, auditing, and data and safety monitoring. ODQ also coordinates quality assurance efforts related to multi-center clinical research.

DF/HCC Clinical Trials Research Informatics Office (CTRIO): A group within DF/HCC responsible for providing a comprehensive data management platform for managing clinical trial data.

16. GENERAL ROLES AND RESPONSIBILITIES

For DF/HCC Multi-Center Protocols, the DF/HCC Sponsor, the Coordinating Center, and the Participating Institutions are expected to adhere to the following general responsibilities:

16.1 DF/HCC Sponsor

The DF/HCC Sponsor, **[name]** will accept responsibility for all aspects of conducting a DF/HCC Multi-Center protocol which includes but is not limited to:

- Oversee the coordination, development, submission, and approval of the protocol as well as subsequent amendments.
- Ensure that the investigators, study team members, and Participating Institutions are qualified and appropriately resourced to conduct the protocol. A current CV will be collected at study initiation.
- Include the Multi-Center Data and Safety Monitoring Plan as an appendix to the protocol.
- Ensure all Participating Institutions are using the correct version of the protocol, as well as current Investigator Brochure or product information.
- Ensure that each participating investigator and study team member receives adequate protocol training (and/or a Site Initiation Visit prior to enrolling participants) and throughout trial's conduct as needed. All site Principal Investigators will sign protocol signature pages at study initiation and each protocol version change.
- Ensure the protocol will be provided to each participating site in a language understandable to all applicable site personnel when English is not the primary language.
- Monitor progress and overall conduct of the study at all Participating Institutions.
- Ensure all DFCI Institutional Review Board (IRB), DF/HCC and other applicable (i.e. FDA) reporting requirements are met.
- Review data and maintain timely submission of data for study analysis.
- Act as the single liaison with FDA (investigator-held IND trials), as applicable. Any delegated Sponsor/Investigator responsibilities (i.e. to CROs, drug distribution

vendor, etc) will be documented and the appropriate regulatory authority will be informed.

- Ensure compliance with all requirements as set forth in the Code of Federal Regulations, applicable DF/HCC requirements, HIPAA requirements, and the approved protocol.
- Commit to the provision that the protocol will not be rewritten or modified by anyone other than the DF/HCC Sponsor.
- Identify and qualify Participating Institutions and obtain accrual commitments prior to extending the protocol to that site.
- Monitor accrual and address Participating Institutions that are not meeting their accrual requirements.

